# **Secondary Objectives:**

 Cumulative incidence of serious adverse events during the study period: transfusion reaction (fever, rash), transfusion-related acute lung injury (TRALI), transfusion-associated circulatory overload (TACO), and transfusion-related infection.

# **Investigational Safety Objectives:**

- 1. Evaluate the safety of treatment with COVID-19 convalescent plasma in relation to the amount of Anti-SARS-CoV-2-spike protein IgA as assayed by the EUROIMMUN Anti-SARS-CoV-2 assay.
- 2. Evaluate the safety of treatment with COVID-19 convalescent plasma in relation to the amount of Anti-SARS-CoV-2-spike protein IgG and IgA as assayed by the EUROIMMUN Anti-SARS-CoV-2 assay.

All primary and secondary safety endpoints for the study will be re-evaluated based on levels of IgA for investigational objective #1 and based on combined levels of IgG and IgA for investigational objective #2

#### 2.2 Data collection

The following data points will be gathered for all patients in the study while inpatient. Patients discharged prior to 28 days will receive a phone call to determine their 28 day outcome and patients enrolled in the study will be monitored for 90 days from discharge to determine if there is a readmission and the reason for the readmission.

**COVID-19 Presentation:** Collected on enrollment, see form on page 30.

**Demographics**: Collected on enrollment, see form on page 31.

Medical History: Collected on enrollment, see form on page 31.

Concomitant Medications: Collected on enrollment, see form on page 31.

Vital Signs: Collected daily from enrollment to discharge, see form on pages 30 and 32. Laboratory Values: Collected daily from enrollment to discharge, patient is required to have a CBC with differential, a CMP, a ferritin and a CRP. On enrollment and weekly the patient must have an IL-6, D-Dimer, procalcitonin, LDH, fibrinogen, ESR, and CK. IL-6 and LDH, other laboratory values will be recorded when obtained through standard of care. See form on page 32.

Clinical Status: Collected daily from enrollment to discharge, see form on page 32.

**Medications:** Collected daily from enrollment to discharge, see form on page 33.

Serology Values: Collected per schedule, see form on pages 34 and 35.

PCR Values: Collected per schedule, see form on page 36

Safety Data: Collected for first 24 hours after transfusion, see form on page 37.

**Outcomes:** Collected at discharge or death, see form on pages 38 and 39.

# 2.3 Study population

#### **Inclusion Criteria for Enrollment**

- 1. Subjects must be 18 years of age or older.
- 2. Hospitalized with confirmed COVID-19 infection via COVID-19 SARS-CoV-2 RT-PCR testing.
- 3. Symptoms consistent with COVID-19 infection (fever, acute onset cough, shortness of breath) at time of screening.
- 4. Patient requires >6L NC O2 (Group A) or intubated (Group B).
- 5. Patient (or their representative) is willing and able to provide written informed consent and comply with all protocol requirements.

#### **Exclusion Criteria**

- 1. Female subjects with positive pregnancy test, breastfeeding, or planning to become pregnant or breastfeed during the study period.
- 2. Receipt of pooled immunoglobulin in past 30 days.
- 3. Contraindication to transfusion or history of prior reactions to transfusion blood products.
- 4. Patients currently undergoing cancer treatment or those who are presently immunocompromised.
- 5. Patient who in the opinion of the investigator will not be a good study candidate.

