# **Study Population:**

Group A: Hospitalized COVID-19 patients ages ≥18 years with respiratory symptoms, requiring >6L of oxygen to maintain O2 saturation >92%. Patient may not require intubation, and may be admitted for no longer than 14 days.

Group B: Hospitalized COVID-19 patients ages ≥18 years requiring intubation.

Study Duration: May 15, 2020 to December 31, 2022

Study Design: This phase 2 trial will evaluate the efficacy and safety of SARS-CoV-2 convalescent plasma as treatment for confirmed COVID-19 respiratory disease (as defined in the inclusion criteria). Adults 18 years of age and older may participate. Patients may be enrolled in group A within 14 days of admission to the hospital and may be enrolled in group B at any time after intubation. A total of 300 eligible subjects with significant oxygen requirements and 200 eligible subjects who require intubation will be included in the study. They will receive convalescent plasma from either a patient who has recovered from COVID-19 or from an asymptomatic carrier with confirmed IgG against SARS-CoV-2. Subjects will not be randomized but the amount of anti-SARS-CoV-2 IgG and IgA in any unit of plasma will not be known when the unit is assigned to the patient. This will allow us to examine the relationship between the amount of anti-SARS-CoV-2 antibody and outcomes. Analysis will be based on measurement of optical density of the IgG level in the unit of plasma the patient is randomly supplied by the blood bank. While investigators and patients will be aware the patient is receiving a unit of COVID-19 convalescent plasma, both the investigators and the patients will be blinded to the antibody content of that unit.

Assessment in all subjects: Given the issues with the pandemic such as limitations on PPE, and the need for strict isolation, patient data will be limited to that which is acquired from the EPIC EMR (in use at our institution) but not from face to face interview with the patient. The data will be supplemented as possible with phone interview with the patient or their LAR. Consenting will be e-consent based using RedCap with the consent form e-mailed to the patient or the LAR for review prior to the actual consent process. Consent will be obtained over the phone and with a witness: the consent provider and the witness will both document the consent process within the patient's chart in the EPIC EMR.

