#### 2.5 Treatment

All study participants will receive 1 unit of the study product. There is no re-dosing of the product within this study. There is no formal randomization, but both the patient and the study team will be blinded to the amount of anti-SARS-CoV-2 antibodies found in the unit of plasma assigned to the participant. The blind will be maintained until study closure and formal data analysis.

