#### 2.6 Rationale for Dose

Review of the literature using COVID-19 convalescent plasma reveals that there is currently no standard dose or schedule for giving convalescent plasma. In addition there is currently no standard assay for antibody level performed on plasma in the United States and there is no way to guarantee access to more than one unit of plasma at a time or guarantee that if more than one unit were available they would be comparable in antibody content. As such the dose was chosen via the pragmatic approach of using a single unit of plasma and stratifying the results by the serological assay of that unit.

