#### Confidentiality

Risks for this study include breach of confidentiality. To minimize this risk all case forms will use a code consisting of a unique number. A list will be kept that links the patient's name and health system medical record number to the code. This list will be kept in a securely in the RedCap database which will be used to store patient date. Only study personnel will have access to the list and the case report forms. A list of the patients involved in the study will be kept within the EPIC EMR in order to facilitate access to the patient's records for purposes of the study and to prevent recruitment of patients who are already in the study. The list will be private, maintained by the study principal investigator at each site with their lead coordinator, and accessible only to appropriate study personnel.

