# **Maintenance of Confidentiality:**

All appropriate measures will be taken to protect the identity of subjects and the confidentiality of collected data.

Data will be collected using study-specific source documents which are included in this document. The data will be stored in the RedCap database, a secure hospital-based computer system with password protection. The author of an entry is easily identifiable, and the system is such that editing of documents and the person who edited it is tracked. The study personnel responsible for data collection will be trained to ensure reliability and quality of the data and the data will be monitored by the Beaumont Research Coordinating Center. All patient identifiers will be removed from the collected data to ensure HIPAA compliance and patient confidentiality. Patient data will be identified using initials and a patient study number. Any communication relating to the study, study documents, and electronic databases will identify patients by initials and their assigned number only.

A patient identification log will be kept permitting easy identification of each patient during and after the study. The patient identification log will be confidential and will be kept in a secure location in the study office. To ensure confidentiality, no copy will be made. The log will link the patient's name and medical record number to the unique study identification number. An electronic list of patients in the study, only available to study personnel, will be kept within the EPIC EMR of our health care system for use in rapidly accessing the patient's health information for purposes of the study and to assure that no patient is recruited to the study more than once. When the study and all

review is complete, the list linking the study code to identifiers will be destroyed and the patient list within the EMR will be deleted.

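### The antibody washout omits convalescent plasma, so a patient already given a non-study unit is eligible and the study unit's IgG is only part of that patient's passive antibody

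*Combined protocol and SAP*

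**What the plan says.** Section 2.6 (Rationale for Dose) describes the design as "using a single unit of plasma and stratifying the results by the serological assay of that unit". Section 3.1 makes IgG level the main independent variable in both primary logistic models, with age, gender and race as covariates. Its sensitivity analysis adds comorbidities one at a time. Neither analysis includes earlier plasma or the patient's own baseline IgG.

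The provisions that might keep out a previously transfused patient are these:

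- Section 2.3, exclusion 2: "Receipt of pooled immunoglobulin in past 30 days".
- Section 2.3, exclusion 3: "Contraindication to transfusion or history of prior reactions to transfusion blood products". This concerns reactions and contraindications, not prior receipt.
- Section 2.3, exclusion 5: "Patient who in the opinion of the investigator will not be a good study candidate".
- Section 2.5: "There is no re-dosing of the product within this study".
- Section 4.1, Confidentiality: the EMR list exists in part "to prevent recruitment of patients who are already in the study". Maintenance of Confidentiality gives the same purpose, that "no patient is recruited to the study more than once".

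On timing, the protocol summary admits Group A patients up to 14 days after admission and says patients "may be enrolled in group B at any time after intubation".

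**The concern.** Exclusion 2 shows an intention to keep out patients who recently received passive antibody. A single-donor convalescent unit is not pooled immunoglobulin, so the exclusion misses the product that carries the antibody under study. The re-dosing rule and the enrolment list look only inside this trial. A patient given convalescent plasma before enrolment, off protocol or at another hospital, therefore meets every listed criterion unless an investigator chooses to apply exclusion 5.

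That patient is analysed by the IgG of the study unit, although an earlier and unmeasured unit also contributed. A patient recorded at low IgG may already have had a high-IgG unit, which weakens the IgG-outcome association. Patient IgG before transfusion, the first time point of secondary endpoint 15, would contain donor as well as native antibody and cannot by itself separate them. Section 2.6 justifies a single unit partly because several units might differ in antibody content. An earlier non-study unit brings that problem back.

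**Working it through.** **1. Does any provision close the gap?** Taken in turn, exclusion 2 covers a different product and exclusion 3 a different question (reaction, not receipt). The re-dosing rule and the EMR list are confined to this study. Exclusion 5 is discretionary and nothing directs it at earlier plasma. No planned covariate or analysis accounts for it. The gap is real on the text.

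**2. The plan's own power figures.** Section 3.2 states 87.8% for N = 200 (28-day survival 25% to 50%) and 87.9% for N = 300 (intubation 38% to 18%). Both come from a step in risk, mostly at IgG 5, analysed as linear in IgG. The IgG distribution is not given, so exact reproduction is impossible. Simulation with IgG assumed Uniform(0,10), two-sided 5%, gives 88.9% for Group B (and 73.1% against the stated 74.4% for survival of 45%), but 92.2% for Group A. Normal(5,2) gives 87.9% for Group A and 83.6% for Group B. The stated figures are plausible and are not disputed here.

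**3. Dilution in Group B.** Assumptions: a share q had an earlier unit; half of those units exceed the threshold; such a unit gives the full benefit; earlier plasma is unrelated to study-unit IgG.

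- Survival with a low-IgG study unit = 0.25 + q × 0.5 × 0.25.
- High-minus-low difference = 0.25 × (1 − q/2).
- Approximate effective sample size = 200 × (1 − q/2)².

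For power, start from the stated 87.8%, which corresponds to a standardised effect of 1.960 + 1.165 = 3.125. Multiply by (1 − q/2) and by √(0.4375/V). Here V is the sum of p(1 − p) over low and high groups of equal size, and 0.4375 = 0.25 × 0.75 + 0.50 × 0.50 is its value at q = 0. Power = Φ(result − 1.960).

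| q | Low-unit survival | Difference | Effective N | V | Standardised effect | Power |
|---|---|---|---|---|---|---|
| 0 | 25.0% | 25.0 points | 200 | 0.4375 | 3.125 | 87.8% |
| 5% | 25.6% | 24.4 | 190 | 0.4406 | 3.036 | 85.9% |
| 10% | 26.25% | 23.75 | about 180 | 0.4436 | 2.948 | 83.8% |
| 20% | 27.5% | 22.5 | 162 | 0.4494 | 2.775 | 79.2% |

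**4. Check by simulation.** The settings were Uniform(0,10) IgG, an earlier unit from the same distribution, and analysis on the study unit only. If the two units' IgG adds, Group B power is about 89%, 86%, 84% and 78% at q = 0, 5%, 10% and 20%. If only the larger unit counts, it is about 90%, 87%, 85% and 81%. Group A under the additive version falls from about 92% to 90%, 88% and 85%. Normal(5,2) is less favourable: at q = 20%, additive power is about 67% in Group B and 74% in Group A, from about 84% and 87% at q = 0.

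**The case against.** The best counter-argument is that nothing shows this happens often. The documents describe no off-protocol plasma route and give no transfer figures. What they do say suggests scarcity: section 2.6 cannot guarantee access to more than one unit at a time, and section 1.5 cites a series in which only 6 of 21 eligible patients were treated. The open Group B window makes earlier plasma possible but does not measure it. At q of 5% to 10% the loss is 0.6 to 1.25 points of difference. Crediting an earlier unit with full benefit may also overstate dilution, since Group B patients are still intubated at entry. All of this stands, and it limits the size of the point but does not remove it.

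Partial data capture also deserves credit. The enrolment form appears to request treatments given during the current admission, although its text is broken. Blood products are appended to the daily form, and pre-transfusion IgG is drawn. However, the daily form starts at enrolment, plasma given at another hospital is not shown to be captured, and no criterion or analysis uses these data.

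A reader might infer more than the documents support:

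- *That unit IgG fails as the exposure for the whole trial.* It does not. Patients without earlier plasma are unaffected.
- *That the omission could create a false association.* Unit IgG is unknown at assignment, so earlier plasma should not track it. Dilution is the expected direction.
- *That acute reactions could not be tied to the study unit.* The safety form uses windows of 2, 4, 6 and 24 hours after transfusion, and the cytokine-storm endpoint uses 48 hours. A unit given days before would not generally prevent attribution.

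**Conclusion.** The point holds as a correctable gap in eligibility. As written, the criteria admit patients whose passive antibody is only partly described by the trial's single exposure variable, and no planned analysis deals with them. The expected harm is attenuation in both primary analyses and a pre-transfusion patient IgG that mixes two sources.

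The size depends on q, which the documents do not give. Under the stated assumptions the Group B cost is about 2 percentage points of power at q = 5%, 4 at 10% and 8 to 9 at 20%. It would be larger if doses add or IgG values cluster near the threshold, and smaller if earlier units had little effect. This is not a fatal flaw. It merits a change because the amendment is short and protects the only contrast the trial has.

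**What to change.** Extend exclusion 2 so that, besides pooled immunoglobulin, it covers prior receipt of COVID-19 convalescent plasma or any other anti-SARS-CoV-2 antibody product, at this or any other hospital. Use the look-back window already in that item. Verify it at screening from the EMR, transfer records and the history given by the patient or LAR.

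Record non-study convalescent plasma given after enrolment and report it descriptively, keeping those patients in the primary analysis. Dropping them would condition on an event after treatment that may reflect deterioration, and censoring has no meaning in a logistic model of a binary outcome.

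The cost is one line in the eligibility criteria, a short screening check, one sentence on reporting and the loss of a few previously transfused candidates. The power calculation then stays at its q = 0 value as far as earlier plasma is concerned.

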#### 2.4 Schedule of events

Study Period	Screening	Baseline	Treatment		Follow Up a					
Day	-1 to 0	0	0	D	1	3	7	14	21	28
Eligibility								,	,	
Inclusion/Exclusion	Х									
Informed consent	Х									
Demographics and	V									
medical history form	X									
Initial data collection	Х									
form	^									
Type and Screen	Х									
Pregnancy Test	Х									
Study Procedures										
Plasma transfusion			X							
Vital signs			Xp							
Physical exam c	X		Xd		Χ		Χ			
Daily vital signs, clinical										
and laboratory values				Χ						
form										
Daily medications form				Χ						
Adverse event		X	X	Х						
monitoring				^						
Serology collection form		X	X		Χ	Χ	Χ	Χ	Χ	Xe
Outcome form										Xf
Laboratory Testsg				_	•	,	,			•
CBC with differential		X		Χ						
CMP		Χ		Χ						
Ferritin		Χ		Χ						
Fibrinogen		Χ					Χ	Χ	Χ	Χ
CRP		Χ		Χ			Χ	Χ	Χ	Χ
ESR		Χ					Χ	Χ	Χ	Χ
Creatine Kinase		Χ					Χ	Χ	Χ	Χ
D-Dimer		Χ					Χ	Χ	Χ	Χ
LDH		Х					Χ	Χ	Χ	Χ
Interleukin-6		X					Χ	Χ	Χ	Χ
Triglycerides		Χ					Χ	Χ	Χ	Χ
Procalcitonin		Χ					Χ	Χ	Χ	Χ
Anti-SARS-CoV-2 IgA			X h		Χ	Χ	Χ	Χ	Χ	Xi
Anti-SARS-CoV-2 IgG			X h		Χ	Χ	Χ	Χ	Χ	Xi
SARS-CoV-2 RT PCR			Xj		Χ	Χ	Χ	Χ		

- a Column D are obtained daily, day 1 and 3 are obtained 24 hours (+/- 1 hour) from transfusion end, day 7, 14, 21, and 28 are obtained any time on that calendar day.
- b Standard vital signs for transfusion of blood products will be performed.
- c Given the issues with isolation and PPE, the exam of the attending physician's team or the pulmonary critical care team can be used.
- d Only if needed due to acute reaction.
- e After 28 days will be collected every 7 days +/- 1 day till discharge.
- f Outcome form to be filled out on final day of admission if prior to 28 days or at 28 days, after 28 days a second outcome form to be filled out on final day of admission, readmission will be tracked for 90 days.
- g All laboratory tests from this list which are obtained as standard of care will be tracked, baseline labs within 24 hours are acceptable and do not need to be reordered.
- h To be drawn within 1 hour prior to transfusion and 1 hour post-transfusion completion (no earlier than 1 hour but up to 75 min post transfusion).
- i After day 28 this will be drawn every 7 days +/- 1 day while participant remains hospitalized.
- j To be obtained within 1 hour prior to transfusion.

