# **Group A Primary Efficacy Endpoint:** Avoidance of intubation at 28 days. **Group A Secondary Efficacy Endpoints:**

- **1.** Final outcome on a 7-point ordinal scale
- **2.** Cardio-circulatory arrest (at any time)
- 3. Renal failure, as measured by RIFLE criteria
- 4. Liver failure, as measured by elevation of ALT and AST to 5x the upper limit of normal or significant worsening of current liver failure with rise in transaminases of >25%
- 5. Evidence of cytokine storm based on measurement of inflammatory markers
- **6.** Type and duration of respiratory support
- 7. Requirement of pressor support
- 8. ICU mortality
- **9.** ICU length of stay
- **10.** In hospital mortality
- **11.** 28-day mortality
- **12.** Length of stay
- **13.** Ventilator-free days
- **14.** Readmission rate
- **15.** Patient level of anti-SARS-CoV-2 IgG at the following times: prior to transfusion, 1-hour post-transfusion, 24 hours post-transfusion, 72 hours post-transfusion, 7 days post-transfusion, every 7 days until discharge, day of discharge.
- **16.** Evaluate the rates, levels (based on CT values) and duration of SARS-CoV-2 RNA in nasopharyngeal swabs using RT-PCR amongst the anti-SARS-CoV-2 convalescent plasma at the following times: prior to transfusion, 24 hours post-transfusion, 72 hours post-transfusion, 7 days post-transfusion, and 14 days post-transfusion.

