# **ABACCuS Serology Data Collection Form:**

Patient Initials/Study ID: _		Date of Enrollment:	
Plasma Unit Used:		Date and Time of Transfusion	:
Patient Baseline Serology	:		
IgA OD:	IgG OD:	Date and Time of Specimen:	
Patient Serology 1 Hour P	ost-Transfusion (+/- 5 min)		
IgA OD:	lgG OD:	Date and Time of Specimen:	
Patient Serology 24 Hours	s Post-Transfusion (+/- 1 hour)		
IgA OD:	lgG OD:	Date and Time of Specimen:	
Patient Serology 72 Hours	s Post-Transfusion (+/- 3 hours)		
IgA OD:	IgG OD:	Date and Time of Specimen:	
Patient Serology 1 Week F	Post-Transfusion (+/- 1 day)		
IgA OD:	IgG OD:	Date and Time of Specimen:	
Patient Serology 2 Weeks	Post-Transfusion (+/- 1 day)		
IgA OD:	IgG OD:	Date and Time of Specimen:	
Patient Serology 3 Weeks	Post-Transfusion (+/- 1 day)		
IgA OD:	IgG OD:	Date and Time of Specimen:	
Patient Serology 4 Weeks	Post-Transfusion (+/- 1 day)		
IgA OD:	IgG OD:	Date and Time of Specimen:	
Patient Serology Day of D	ischarge		
IgA OD:	IgG OD:	Date and Time of Specimen:	
Signature of coordinator		 Date	
 			
Signature of Investigator re	eviewing data	Date	

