# ABACCuS SARS-CoV-2 RT PCR Data Collection Form:

Patient Initials/Study ID: _		Date of Enrollment:
Plasma Unit Used:		Date and Time of Transfusion:
Patient Qualifying RT PC	R:	
Result:	CT Value:	Date and Time of Specimen:
Patient Pre-Transfusion F	RT PCR:	
Result:	CT Value:	Date and Time of Specimen:
Patient 24 hour Post-Tran	nsfusion RT PCR:	
Result:	CT Value:	Date and Time of Specimen:
Patient 72 hour Post-Tran	nsfusion RT PCR:	
Result:	CT Value:	Date and Time of Specimen:
Patient 7 Days Post-Tran	sfusion RT PCR:	
Result:	CT Value:	Date and Time of Specimen:
Patient 14 Days Post-Tra	nsfusion RT PCR:	
Result:	CT Value:	Date and Time of Specimen:
Signature of coordinator		 Date
engination of occidentation		Dato
Signature of Investigator	reviewing data	Date

ABACCuS 28 Safety Form:					
Patient Initials/Study ID:	Date of Enrollment:				
Plasma Unit Used:	Date and Time of Transfusion:				
In the 2 hours after the transfusion: Did the patient have a rapid decline in respiratory status: Y	/N				
If yes: Date and Time:	Severity:				
If yes: Description of the event:					
Did the patient have a rapid decline in clinical status: Y/N					
If yes: Date and Time:	Severity:				
If yes: Description of the event:					
In the 4 hours after the transfusion: Did the patient have a fever of >38 $^{\circ}$ C: Y/N $T_{max}$ : _	If yes: Date and Time:				
Did the patient have an allergic reaction: Y/N  Conjunctival Edema: Y/N Edema of Oral Area: Y/N  Generalized Flushing: Y/N Hypotension: Y/N  Maculopapular Rash: Y/N Pruritus (itching): Y/N  Urticaria (hives): Y/N	Localized Angioedema: Y/N				
In the 6 hours after the transfusion: Was the patient diagnosed with Transfusion Associated Cir	rculatory Overload (TACO): Y/N				
If yes: Date and Time:	Severity:				
Was the patient diagnosed with Transfusion Related Acute	Lung Injury (TRALI): Y/N				
If yes: Date and Time:	Severity:				
In the 24 hours after the transfusion: Did the patient have evidence of cytokine storm: Y/N					
If yes: Date and Time:	Severity:				
If yes: Description of the event:					
Signature of coordinator	Date				
Signature of Investigator reviewing data	Date				

ABACCuS 28 Day Ou	tcome Form Gro	oup A:						
Patient Initials/Study ID:			Date of Enrollment:					
Plasma Unit Used:			Date a	Date and Time of Transfusion:				
Primary Outcome:								
Was the patient intuba	ted within 28 days	s of the transfus	ion: Y/N					
If intubated: Date of intubation:				Day #:				
Secondary Outcomes	5 :							

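### The schedule footnote times the day-3 sample at 24 hours where the endpoints and forms require 72 hours, and the other sampling windows and the time anchor also need reconciling

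*Combined protocol and SAP*

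**What the plan says.** Section 2.4, footnote a, covers both early follow-up columns in one phrase: "day 1 and 3 are obtained 24 hours (+/- 1 hour) from transfusion end". Days 7, 14, 21 and 28 may be sampled at any hour of the named calendar day. Footnote h times the serum after transfusion from completion: "no earlier than 1 hour but up to 75 min post transfusion".

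Section 2.1 lists 24 and 72 hours as separate times in both groups. Endpoint 15 (patient IgG) is measured "prior to transfusion, 1-hour post-transfusion, 24 hours post-transfusion, 72 hours post-transfusion, 7 days post-transfusion, every 7 days until discharge, day of discharge". Endpoint 16 (SARS-CoV-2 RNA) is measured "prior to transfusion, 24 hours post-transfusion, 72 hours post-transfusion, 7 days post-transfusion, and 14 days post-transfusion".

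The serology form has separate 24-hour and 72-hour lines. The 72-hour line reads "Post-Transfusion (+/- 3 hours" (closing bracket omitted here), the 1-hour line allows 5 minutes either way, and lines from one week onward allow 1 day either way. The RT-PCR form also has separate 24-hour and 72-hour lines but prints no tolerances. Both forms carry one transfusion date-and-time entry without saying start or end, and a date and time for every specimen.

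Section 3.1 analyses patient IgG and viral RNA with generalized linear mixed models that have time as a fixed effect. It does not say whether time is the nominal visit or actual elapsed time.

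**The concern.** Sampling windows are operative rules: coordinators draw to them and monitors judge deviations by them. Here the schedule and the forms give different rules for the same specimens, and nothing says which governs. For day 3 the schedule's stated hour belongs to day 1. For the 1-hour serum, neither version is an obvious slip, so a reader cannot settle the matter from context.

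At stake is how consistently specimens are timed across eight hospitals, and whether the same draw is called compliant at one and a deviation at another. The endpoints concerned are 15 and 16. Time is a covariate in their models, so an unclear anchor or mixed windows would enter the analysis directly if nominal times were used.

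**Working it through.** The plan states no figure to reproduce. The check compares the windows as intervals.

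| Sample | Section 2.4 schedule | Serology form |
|---|---|---|
| 1 hour | 60-75 min after completion (footnote h) | 60 ± 5 = 55-65 min |
| Day 1 | 24 ± 1 = 23-25 h (footnote a) | 24 ± 1 = 23-25 h |
| Day 3 | 24 ± 1 = 23-25 h (footnote a, read literally) | 72 ± 3 = 69-75 h |
| Days 7, 14, 21, 28 | named calendar day (footnote a) | ± 1 day |
| After day 28 | every 7 days ± 1 day (footnotes e, i) | ± 1 day |

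1. **Agreement.** The day-1 windows match, and so do those after day 28. The conflicts are in the other three rows.

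2. **Day 3.** The nearest edges are 25 h and 69 h: 69 − 25 = 44 h apart. No serum can satisfy both. The RT-PCR form has no tolerance of its own, so footnote a is the only window given for the day-3 swab.

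3. **Day 3 if only the hour is corrected.** 72 ± 1 gives 71-73 h, which lies inside 69-75 h. But 6 − 2 = 4 of the form's 6 hours (two thirds) would still lie outside the schedule. The tolerance has to be reconciled as well as the hour.

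4. **1-hour serum.** The overlap runs from max(60, 55) = 60 to min(75, 65) = 65 min, a width of 5 min. Of the schedule's 15-minute window, 10 min (two thirds) is outside the form. Of the form's 10-minute window, 5 min (half) is earlier than the schedule permits. These are shares of window width, not predicted deviation rates.

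5. **Days 7 to 28.** If transfusion ends h hours after midnight (0 ≤ h < 24), the named calendar day runs from h hours before the exact weekly mark to 24 − h hours after it. That is always within 24 hours either way, so a draw that follows the schedule satisfies the form. The reverse fails: a draw on the day before or after is allowed by the form and not by footnote a.

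6. **Anchor.** The unit is about 300 mL (Study Product) and the rate is at most 500 mL/hour (section 2.7). A full unit therefore takes at least 300/500 × 60 = 36 min. Start and end differ by more than the ± 5 min or the 15-minute window on the 1-hour serum, and by more than half of the ± 60 min on the 24-hour sample.

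7. **Which endpoints.** The day-3 conflict reaches both endpoint 15 and endpoint 16. The 1-hour and weekly conflicts concern serology only: there is no 1-hour swab, and the RT-PCR form prints no windows.

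**The case against.** The strongest reply is that no one would follow footnote a literally on day 3. The column is headed Day 3, the endpoints list 24 and 72 hours separately, and both forms have a line for each. The footnote reads as a drafting omission that sites can resolve. This largely stands, and it limits the consequence. It does not remove the error, and it does not help with the 1-hour serum, where neither source is plainly wrong.

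Four stronger readings are tempting, and the documents do not support them.

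- *The 72-hour point will be lost.* Read literally, footnote a would leave four distinct RNA times out of five and widen the gap before day 7 from 4 days to 6. That requires sites to ignore the column heading, the endpoint lists and both forms, so it is not a realistic expectation.
- *Valid samples will be flagged or discarded, two thirds of them at 1 hour.* No section says that an out-of-window specimen is rejected or excluded. The two-thirds and one-half shares become rates only if draws are spread evenly over the windows, which nothing in the documents establishes. Nor do they show that 5 to 10 minutes would alter the IgG result.
- *Every correct 1-hour draw will fail the form.* If the start were recorded, a draw 60 min after completion would lie at least 36 + 60 = 96 min later. But the schedule refers to transfusion end or completion, so staff may well record that, and an infusion can be stopped early. What stands is that the form does not say which time it wants.
- *The models use nominal day.* Section 3.1 does not say so. Actual specimen times are collected on both forms, so elapsed time can be used once the anchor is fixed.

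**Conclusion.** The contradictions are real and in operative text. The schedule's day-3 rule is wrong as written against the study's own endpoints and forms, with disjoint windows (23-25 h against 69-75 h). The 1-hour windows share only 5 minutes, the windows for days 7 to 28 are nested in one direction only, and the transfusion time on the forms is ambiguous by at least about 36 minutes for a full unit.

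The likely consequence is modest: inconsistent sample timing and inconsistent deviation classification for secondary endpoints 15 and 16. This assumes that most sites would infer 72 hours from the column heading and forms. The primary endpoints (intubation and 28-day mortality), the IgG measured in the plasma unit and the sample size are untouched. It is a minor correction, worth making because it is cheap and because an end time left off the study form may be hard to recover later.

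**What to change.** - In section 2.4, separate day 1 from day 3 in footnote a and give day 3 the 72-hour time that the endpoints and forms already use, with one tolerance shared with the serology form.
- Reconcile footnote h with the 1-hour line of the serology form, and footnote a with that form's weekly lines, so that each sample has one nominal time, one tolerance and one anchor. Print the same windows on the RT-PCR form where they apply.
- Record the time the transfusion ended as a labelled field on both forms.
- State in section 3.1 that the mixed models for patient IgG and viral RNA use actual elapsed time from transfusion end, computed from the specimen times already collected.

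The cost is footnote and form wording, one extra time field and one derived variable. No additional samples or patients are needed.
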